## Study Summary

Title	A Randomized Prospective Evaluation of Four Injectable Neuromodulators in the Glabella Area: Randomized Controlled Trial
Short Title	Glabella 4 Toxin Study
IRB Number	849045
Protocol Number	NCT05167864
Methodology	Randomized Control Trial
Study Duration	18 months
Study Center(s)	Single-center.
Objectives	To quantify the dynamic strain of four commonly available neuromodulators injected in the glabellar area over time as well as correlate patient satisfaction to the change in dynamic strain over time.
Number of Subjects	Approximately 140
Main Inclusion and Exclusion Criteria	
Inclusion criteria:
 

1) Women ages 30-65

2) No neuromodulator treatment within 12 months

3) Have not undergone cosmetic procedures to the upper face above the malar region (cheekbone area).

 
Exclusion:
 

1) Men

2) Patients who have previously been treated with a neuromodulator<12 months

3) Over 65 or under 30 years of age

4) Those with a prior known condition that affects facial animation (such as stroke, palsy),

5) Cannot be actively taking blood thinners,

6) Presence of eye ptosis

7) Autoimmune disease

CONFIDENTIAL

Intervention	Randomization to one of four neuromodulator glabellar injections: 1) onabotulinumtoxinA 2) abobotulinumtoxinA 3) incobotulinumtoxinA 4) PrabotulinumtoxinA
Statistical Methodology	Descriptive statistics will be used to describe variables of interest. Fischer's exact test and Chi-square will be used to compare categorical variables, and linear regression will be used for continuous variables.
Data and Safety Monitoring Plan	PI will oversee the study, protocol, and data monitoring and storage.

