### **2.1 Primary Objective**

To compare the efficacy of four commonly available neuromodulators using 3D imaging to quantify dynamic strain measurements

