### ***3.4 Study Endpoints***

#### **3.4.1 Primary Study Endpoint**

The primary endpoint is to quantify the change in dynamic strain of the glabella area after injection of four neuromodulators using 3D facial imaging measurements over time.

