#### **3.4.2 Secondary Study Endpoints**

- 1) Quantify the change in the dynamic strain of the glabella area after injection between the four neuromodulators
- 2) Quantify the change of dynamic strain measurements of each facial animation over time.
- 3) Correlation of satisfaction as determined by the FACE-Q to the degree of dynamic strain overtime

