#### **6.2 Statistical Methods**

The primary analysis will be done using chi-squared testing and Fischer's exact test for categorical variables, where applicable, and the paired t-test for continuous variables. Analysis is preformed blinded at the end of the study. There is no interim analysis.

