##### **6.3.2 Analysis of Primary Outcome of Interest**

The primary analysis will be done using chi-squared testing and Fischer's exact test for categorical variables, where applicable, and the paired t-test for continuous variables.

CONFIDENTIAL

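### The Summary and Section 6 name different methods for continuous variables, and the only one that can compare the four products has no stated outcome, terms or handling of repeated images

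*Combined protocol and SAP*

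**What the plan says.** The Study Summary, under Statistical Methodology, states that "linear regression will be used for continuous variables". It does not mention a paired test. Section 6.2 assigns the primary analysis of continuous data to "the paired t-test for continuous variables. Analysis is preformed blinded at the end of the study". Section 6.3.2, which is headed as the analysis of the primary outcome, repeats "the paired t-test for continuous variables". Section 6 does not mention regression.

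Strain is continuous and is the subject of the main aims:

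- Primary objective (2.1): "To compare the efficacy of four commonly available neuromodulators using 3D imaging to quantify dynamic strain measurements".
- Primary endpoint (3.4.1): "quantify the change in dynamic strain of the glabella area after injection of four neuromodulators using 3D facial imaging measurements over time".
- Secondary endpoint 1 (3.4.2): "Quantify the change in the dynamic strain of the glabella area after injection between the four neuromodulators".

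Sections 3.1 and 3.2 assign each woman to one of four products. She is imaged before injection and again at Days 3, 30, 90 and 180. No section mentions a random effect, a within-woman covariance, clustered standard errors or a mixed model.

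**The concern.** Two different methods are named for the same class of variable, and the choice affects what can be answered. The Section 6 test looks only within a woman. The comparison of products, which is why the trial is randomised, has no test in Section 6, so an analyst must turn to the Summary's regression. The plan leaves that regression almost wholly open: it does not say whether the outcome is strain or change in strain, whether visits are pooled or taken singly, or how five images from the same woman are handled.

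Some ways of filling the gap are sound. Others treat repeated images of one woman as if they came from different women, which makes standard errors for product differences too small and raises the chance of declaring a difference that is not there. As written, the choice could be made after the data are seen.

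**Working it through.** **1. Which named method can answer which question**

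| Question | Paired t-test (6.2, 6.3.2) | Linear regression (Summary) |
|---|---|---|
| Change from baseline within one product | Yes | Yes, if fitted to change scores |
| Difference between the four products | No: different women, no pairs | Yes, with a product term, but no terms are stated |
| Course over several visits | One visit at a time | Yes, but the handling of repeated images is not stated |

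Four separate within-product paired tests do not fill the gap. One product reaching significance and another not is no test of the difference between them.

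**2. Inputs for the illustration**

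- Women per arm: 140 / 4 = 35 (Sections 4.2 and 3.2).
- Follow-up images per woman: m = 4 (Section 3.1).
- Within-woman correlation rho: not in the documents; assumed 0.3, 0.5 and 0.7.
- Compound symmetry (the same correlation between any two visits) and a two-sided 5% level: assumed.

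The plan gives no figure of its own on this point to reproduce.

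**3. Regression on product and visit, all four follow-up images as independent rows, no true product difference**

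The true variance of a product mean exceeds the one the model assumes by the design effect DE = 1 + (m − 1) × rho. The actual false-positive rates are then approximately:

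- one pair of products: 2 × [1 − Φ(1.96 / √DE)]
- overall test on 3 degrees of freedom: P(χ²₃ > 7.815 / DE)

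| rho | DE | One pair, formula | One pair, simulated | Overall, formula | Overall, simulated |
|---|---|---|---|---|---|
| 0.3 | 1 + 3 × 0.3 = 1.9 | 15.5% | 15.3% | 25.0% | 24.7% |
| 0.5 | 1 + 3 × 0.5 = 2.5 | 21.5% | 21.3% | 37.3% | 37.2% |
| 0.7 | 1 + 3 × 0.7 = 3.1 | 26.6% | 26.4% | 47.2% | 46.2% |

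The simulations used 4,000 null trials per setting with 35 women per arm. The formulas do not involve arm size, so losing 15% of women (140 × 0.85 / 4 = 29.75, about 30 per arm) changes little: simulated overall rates at 30 per arm were 24.7%, 36.0% and 47.7%.

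**4. The same regression on change from baseline, all four changes pooled**

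All four changes share one baseline. With unit variances, the variance of a change is 2(1 − rho). The covariance of two changes is rho − rho − rho + 1 = 1 − rho. Their correlation is (1 − rho) / [2(1 − rho)] = 0.5 whatever rho is. So DE = 2.5, and the rates are about 37% overall and 21% for one pair. Moving to change scores does not help if the visits are still pooled as independent rows.

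**5. Regression of one change score per woman on product, at a single visit**

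Here m = 1, so DE = 1 and the false-positive rate is the nominal 5%. Within one product, an intercept-only regression on change is the paired t-test itself: in a numerical check both gave t = 2.478.

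**The case against.** The strongest reply is that the faulted model is not in the plan. The Summary lists no model terms, so a reader who says that its regression leaves out the woman is supplying product and visit and then charging the plan with the missing term. This stands: a subject term is unspecified, not ruled out. The endpoints are also worded as change in strain, and change regressed on product one visit at a time is valid. The percentages above therefore describe one possible fit, not a stated choice.

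A second reply is that Section 6 is the specific text for the primary outcome, and that the Summary's regression may be meant for the FACE-Q correlation with strain. That is plausible, but the Summary does not restrict it in that way. If it were so restricted, the plan would name no method at all for comparing products on strain.

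Two stronger readings are tempting. A reader might infer that the trial's conclusion on strain turns on which of the two methods is run. The documents do not support that: for product differences the paired test is not a rival route, because it cannot address them, and for within-product change a regression on change scores gives the same answer. A reader might also infer a loss of power from analysing baseline against follow-up without pairing. That would require ignoring Sections 6.2 and 6.3.2, which both prescribe pairing, so it is remote.

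**Conclusion.** The concern holds as a conflict between the Summary and Section 6, together with a gap: Section 6 has no test for the product comparison that the primary objective and secondary endpoint 1 require, and the Summary's regression is too loosely stated to supply one.

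The size is conditional on the fit. It runs from the nominal 5% (one change score per woman at a single visit) to about 25% to 46% for the overall test and 15% to 26% for one pair (four follow-up images as independent rows). The upper figures rest on an assumed correlation of 0.3 to 0.7 and compound symmetry, neither of which is in the documents. The plan should be changed because its wording admits both ends of that span. It does not show that the invalid fit was intended.

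**What to change.** State one method for strain, in the same words, in the Summary, Section 6.2 and Section 6.3.2. Suggested text:

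*Strain at Days 3, 30, 90 and 180 will be analysed with a linear mixed model with product, visit and product-by-visit interaction as fixed effects, baseline strain as a covariate, and an unstructured within-woman covariance. Product differences will be reported by visit with 95% confidence intervals. The paired t-test will be used only for change from baseline within a product. Ordinary linear regression will be used only where each woman contributes one value.*

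A regression of change on product at a single named visit would also be valid, but it would leave the over-time part of the endpoint to separate analyses. The mixed model covers all four visits at once.

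The cost is a few sentences in three places and slightly more analysis work in standard software, with no new data or patients. Intervals for product differences will be wider than a pooled regression would give, because they will reflect the number of women and not the number of images.

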## Background and Study Rationale

### 1 Introduction

This study will be conducted in full accordance with all applicable University of Pennsylvania Research Policies and Procedures and all applicable Federal and state laws and regulations including *[as applicable include the following regulations as they apply 45 CFR 46, 21 CFR Parts 50, 54, 56 All episodes of noncompliance will be documented.]*

The purpose of the study is to use 3D imaging to evaluate the effects of four FDA approved neuromodulators on facial lines, wrinkles and animation. Participation is available to women who have never had a cosmetic procedure above the malar region nor a treatment with a neuromodulator within 12 months. All subjects will undergo 3D imaging using the VECTRA M3 (Canfield Scientific, Inc, Fairfield, NJ) prior to treatment with a neuromodulator in order to determine their baseline dimensions. Imaging will be repeated post injection to determine change over time.

#### 1.1 Background and Relevant Literature

With an annual rise and over 845% increase since the year 2000, botulinum toxin neuromodulation is the most commonly performed minimally invasive technique in cosmetic surgery [1]. In accordance, much research has been produced evaluating the characteristics and efficacy of the various toxin-strain modalities currently available for use [2-4].

One such method for evaluation involves 3D photogrammetry. This technology involves for high level feature enhancement and microscopic anatomical evaluation that was not previously possible [5]. 3D photogrammetry has been used for a range of studies in cosmetic and reconstructive medicine and surgery, including its use in evaluating minimally invasive injection efficacy [6-8].

CONFIDENTIAL

In spite of the research, there are few FDA approved neuromodulators for the treatment of dynamic rhytids, most of which have been available for a period of time and have been clinically described [8]. More recently, a newer neuromodulator, PrabotulinumtoxinA, has received FDA approval, although few studies have captured its onset and effect compared to currently available neuromodulators [9]. We aim to assess onset and quantify the efficacy of four neuromodulators to help determine appropriate treatment selection.

## **2 Study Objectives**

The overall study object is to quantify the dynamic strain of four commonly available neuromodulators using 3D imaging as well as other potential physical measurements differences over time.

### **2.1 Primary Objective**

To compare the efficacy of four commonly available neuromodulators using 3D imaging to quantify dynamic strain measurements

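### The primary objective compares four products, but the plan specifies no between-product test, reference arm, alpha or multiplicity rule for the six possible pairs

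*Combined protocol and SAP*

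**What the plan says.** The primary objective in 2.1 is comparative: "To compare the efficacy of four commonly available neuromodulators using 3D imaging to quantify dynamic strain measurements". Section 1.1 gives the use of the result: "We aim to assess onset and quantify the efficacy of four neuromodulators to help determine appropriate treatment selection". The design randomizes equally to four active products (3.1, 3.2). There is no placebo arm, and no product is named as the reference.

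The endpoints are ordered differently. Section 3.4.1 reads "The primary endpoint is to quantify the change in dynamic strain of the glabella area after injection of four neuromodulators using 3D facial imaging measurements", followed by the words that make it a change over time, with no single visit named. The contrast between products is the first secondary endpoint in 3.4.2: "Quantify the change in the dynamic strain of the glabella area after injection between the four neuromodulators".

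On analysis, 6.3.2 says "The primary analysis will be done using chi-squared testing and Fischer's exact test for categorical variables, where applicable, and the paired t-test for continuous variables", and 6.2 says the same. The Study Summary differs: "linear regression will be used for continuous variables". It gives no model terms, overall test or contrasts. Section 6.2 adds "Analysis is preformed blinded at the end of the study. There is no interim analysis". No significance level, order of testing or multiplicity adjustment is stated anywhere.

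**The concern.** Followed as written, the plan cannot answer its own primary objective. A paired t-test of baseline against follow-up within an arm shows whether strain changed in that arm. Four such tests do not compare the arms: a significant change under one product and a non-significant change under another is not evidence that the two differ.

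Some between-product analysis will therefore have to be chosen that the plan does not describe. Four arms give six pairs, and nothing says which of them decides the trial. Section 1.1 draws attention to the newer product, prabotulinumtoxinA, but no analysis makes it the planned contrast. With no rule, any nominally significant pair could be reported as one product outperforming another, and a reader choosing a treatment could not tell whether that contrast was planned.

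The gap is separate from the lack of a primary visit. Fixing one visit, or replacing the paired test with a between-product test, still leaves six pairs.

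**Working it through.** **Inputs from the documents.** N = 140 (4.2); four arms, equal allocation (3.2); 15% dropout (6.1).

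- Pairs: 4 × 3 / 2 = 6.
- Per arm at enrolment: 140 / 4 = 35. Error df = 4 × 34 = 136.
- Completers: 140 × 0.85 = 119; 119 / 4 = 29.75, about 30 per arm. Error df = 4 × 29 = 116.

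**The plan's own figure.** N = 140 cannot be reproduced, because no alpha, power, effect size or SD is given. There is no planned power to test against.

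**Assumptions.** Two-sided 0.05 per pair (not in the documents, so varied below), one visit, equal SDs, no true product differences, and all six pairs tested without adjustment.

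**Six pairs.** At least one pair is significant when the largest standardized difference exceeds the critical value:

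P(at least one false difference) = P(Q with k = 4 and the error df > √2 × t₀.₉₇₅), where Q is the studentized range. At both sizes t₀.₉₇₅ is about 1.98, so the threshold is 1.98 × √2 = 2.80.

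| Per arm | df | Studentized range | Simulation, separate t-tests |
|---|---|---|---|
| 35 | 136 | 0.2016 | 0.202 |
| 30 | 116 | 0.2013 | 0.202 |

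Treating the six tests as independent gives 1 − 0.95⁶ = 0.265. That is too high, because pairs share arms.

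**Sensitivity to the unstated alpha (30 per arm).**

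| Per-pair alpha | Any false difference over six pairs |
|---|---|
| 0.01 | 4.8% |
| 0.025 | 11.1% |
| 0.05 | 20.1% |
| 0.10 | 35.1% |

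The alpha matters far more than the arm size.

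**Three contrasts against one reference.** At 0.05 each, simulation gives 0.125 (35 per arm) and 0.122 (30 per arm), about 12%.

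**Would an overall F-test be enough?** If all four products are equal, requiring a significant F-test before looking at pairs holds the error at 4.9% to 5.0% (simulated). If one product clearly differs, the F-test will pass, and the other three, if equal, still give a false difference with probability P(Q with k = 3 > 2.80) = 0.122. The pairs themselves need adjustment. Tukey holds the error over all pairs at 5.0% without the F-test.

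**Price of adjustment.** The critical |t| rises from 1.98 to 2.60. The difference detectable with 80% power for one pair (noncentral t, pooled SD) is:

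| Per arm | Unadjusted 0.05 | Tukey |
|---|---|---|
| 35 | 0.674 SD | 0.824 SD |
| 30 | 0.729 SD | 0.892 SD |

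**The case against.** The strongest objection is that 20% is not the error rate of any analysis in this plan. The only continuous-data test in Section 6 is "the paired t-test for continuous variables", which cannot produce six product contrasts. This stands. A reader might infer that the trial as planned carries a 20% false-positive rate. The documents do not support that: the figure shows what the missing rule would permit if all six pairs were tested at 0.05.

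Second, the regression in the Study Summary could supply the overall 3-df test as easily as three contrasts against a reference arm. This also stands. A reader might infer that the reference would be whichever arm the software picks, but that is conjecture. The fair statement is that neither the overall test nor the contrasts are specified.

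Third, if the product comparison is only secondary and the aim is to quantify, multiplicity matters less. This carries some weight given 3.4.1 and 3.4.2, but 2.1 says compare and 1.1 points to treatment selection. The conflict over status is part of the problem.

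Fourth, some hold that comparisons of distinct products need no adjustment. The plan would then still have to say so, name the contrasts and limit its claims; it does none of these.

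Blinded analysis is no defence: testing six pairs of coded arms has the same error rate.

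**Conclusion.** The concern holds in conditional form. The definite finding is a gap in the text: a comparative primary objective, endpoints that place the comparison second, and a primary analysis with no between-product test, alpha, reference, primary pair or multiplicity rule.

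The size depends on what fills the gap. Under no true differences, six unadjusted pairs at one visit would give about 20% at an assumed 0.05 per pair, with a range of 4.8% to 35% for alpha from 0.01 to 0.10. Three contrasts against one reference at 0.05 would give about 12%. These figures do not show that any particular product claim from this trial would be wrong. The change should be made before the analysis, because the result is meant to guide treatment selection and the remedy is cheap.

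**What to change.** 1. Reconcile 2.1 with 3.4.1 and 3.4.2 so that the product comparison is the primary endpoint.
2. Name one primary visit and one expression (frowning strain), and state two-sided alpha 0.05. Without a named visit the rest cannot be applied.
3. In 6.3.2, replace the paired t-test for this comparison with a linear model of follow-up strain, or its change, on product, adjusted for baseline strain. Bring 6.2 and the Study Summary into line. Paired tests may remain as descriptions of change within a product.
4. Report the six pairwise differences with Tukey-Kramer adjusted p-values and simultaneous 95% intervals. Claim a product difference only if its adjusted p-value is below 0.05. The 3-df overall test may be reported but need not be passed first.
5. Alternatively, name one reference product in advance and adjust the three contrasts against it, for example by Dunnett's method.
6. Label product comparisons at other visits and expressions as exploratory.

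The cost is a few sentences, with no new data or patients, and lower sensitivity for any single pair. With Tukey-Kramer, the detectable difference rises by about 0.15 SD at 35 per arm (0.824 − 0.674) and 0.16 SD at 30 per arm (0.892 − 0.729), before any gain from baseline adjustment.

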## **3 Investigational Plan**

### **3.1 General Design**

This study is a randomized controlled trial in which patients will be randomly assigned into one of four groups: those receiving onabotulinumtoxinA (Botox, Allergan, Irvine, California), abobotulinumtoxinA (Dysport, Ipsen Biopharmaceuticals Inc. Cambridge, MA), incobotulinumtoxinA (Xeomin, Raleigh, NC) or prabotulinumtoxinA (Jeuveau, Evolus, Newport Beach, California). Each patient will receive FDA approved dosages in which they are assigned in to treat rhytids within the glabella, as per FDA approved indications. All injections will be performed by a blinded single trained physician ([name]) according to a preset injection plan per FDA approved administration guidelines. Prior to injection patients will be imaged with 3-dimensional photogrammetry. All pre-procedure images will be evaluated for absolute strain performing two types of facial animation: 1) relaxed, and 2) frowning. Subjects will return Day 3, 30, 90, and 180, post intervention for re-imaging with the same expressions. Strain will be calculated using the same metrics.

### **3.2 Allocation to Interventional Group**

Subjects will be randomized to either the prabotulinumtoxinA abobotulinumtoxinA, incobotulinumtoxinA or onabotulinumtoxinA groups. Subjects will be randomized in a one to one fashion using block randomization.

